Vapotherm high velocity therapy (HVT) creates ideally conditioned respiratory gas and delivers it nasally, supporting spontaneous ventilation. This differs from simple oxygen therapy in that the gas is heated, humidified, an exchange of all gasses, including CO₂, is enhanced.^{1,2} Vapotherm technology is unique in its ability to provide this conditioned gas through a small-prong nasal cannula resulting in a high velocity without the well-known adverse effects related to drying and cooling of the nasal mucosa³. This high velocity nasal flow facilitates a well described mechanism of improving ventilatory efficiency by way of eliminating anatomical dead space of the upper airway².

The purging of the nasal cavity is important to alveolar gas exchange because the gas that is drawn to the respiratory regions of the lungs comes from the anatomical reservoir created by the flush, in the same way that oxygen conservation masks can incorporate reservoir bags to reduce the bulk flow requirements from the oxygen source to achieve the same oxygenation effect^{2,4}. Based on mathematical modeling, physiologic studies and clinical observations flow rates of 25 to 35 L·min⁻¹ through Vapotherm's adult cannula purges the anatomical reservoir of the upper airway in the window of time between breaths. Vapotherm's humidification systems are specifically designed to tolerate a high back pressure in the humidification cartridge that is generated by passing these flow rates through small bore cannula resulting in the appropriate flow velocities (turbulent energy)⁴.

Since 2000, HVT has been used extensively and has been well studied.^{2,6} This study is intended as a pilot study utilizing a Wingate-type Exercise Test¹⁸ to evaluate the impact of HVT on reduction of work of breathing and improvement of lactate clearance rate during exercise and the recovery interval. This work may provide foundational data for a larger study and may identify the appropriate parameters for evaluation of physical rehab patients.

II. Overall Study Objective

The **overall objective** of this study is to evaluate the impact of HVT on reduction of work of breathing and change in lactate clearance rate during exercise and recovery during a Wingate-type Exercise test. The study will include four study segments, corresponding to four therapy settings

being tested: (1) FiO₂=100% with Flow=5LPM, (2) FiO₂=21% with Flow=25-30LPM, (3) FiO₂=100% with Flow=25-30LPM, (4) FiO₂=21% with Flow=5LPM.

The **hypothesis** is that HVT, regardless of the oxygen concentration (i.e., FiO₂), will reduce the work of breathing and increase the lactate clearance rate during exercise and recovery intervals.

To test this hypothesis, the study will be conducted with the following specific aims:

Aim #1: Primary Outcome.

The primary endpoint is change in blood lactate from before the exercise test to recovery over a period of 30-60 minutes post-exercise.

Aim #2: Secondary Outcomes.

The secondary endpoints evaluate additional data that may be clinically meaningful. Data will include vital signs (SpO₂, heart rate [HR], respiratory rate [RR], blood pressure [BP]), and perceived level of exertion (BORG [score 0-10]), as measured during the exercise and recovery intervals. Work performance will be computed during test period only, including peak power output, mean power output over 30second intervals, and decrease in power.

Aim #3: Tertiary Outcomes.

The tertiary endpoints will evaluate the participant perceptions of the therapy impact during study procedures: (1) Level of Exertion at Exercise End, (2) Relief of Exertion Recovery End, (3) Comfort/Tolerance of Therapy at Study End [exercise and recovery], as measured on a 1-10 Likert scale.

1. Level of Exertion at Exercise End: "How tired do you feel?"
2. Relief of Exertion at Recovery End: "How fast do you feel you recovered?"
3. Comfort/Tolerance of Therapy at Therapy Segment End: "How comfortable was the therapy while you had it on during exercise? How comfortable was the therapy while you had it on during recovery?"

These **endpoints** will establish the effect of Vapotherm HVNI on lactate clearance, work of breathing, and perceived exertion during exercise and recovery intervals.

III. Participant Selection

Participants will be identified and recruited by study investigators. The study will take place in an appropriate educational forum (e.g., hospital, academic center, laboratory setting, etc.) where kinesiology testing can be accomplished. Initial contact will be made by study investigators, and volunteers may include any interested participants. Participants will be compensated for their time at a rate of approximately **\$50 per hour**.

Inclusion Criteria

1. Adults over 18 years old, in a general state of good health, of either sex
2. No known contraindication to performing a maximal exercise test, i.e., Wingate-type Anaerobic exercise test
3. **Participants must consider themselves able to perform "regular moderate" or "regular strenuous" exercise.**

- a. "Regular moderate" exercise includes less than 30 minutes every day or 30 minutes every other day, of some form of deliberate exercise, that does not include walking.⁷
- b. "Regular strenuous" exercise is 30+ minutes per day, of some form of deliberate exercise, that does not include walking.⁷

Exclusion Criteria

1. Not considered a 'high-performance athlete'
2. Known active cardiovascular, metabolic, liver, or renal disease^{8,9}
3. Orthopedic limitations to exercise¹⁰
4. Pregnancy¹⁰
5. Use of beta-blockers or beta-agonist asthma medications¹⁰
7. Exercise induced asthma
8. Any other health-related issue that would involve the participant's fitness capability
9. Inability to complete all of the study procedures

IV. Study Design

The feasibility/pilot study will be performed as a prospective, unblinded clinical trial of a Wingate-type Anaerobic exercise test. Submaximal cycle ergometry tests are routinely used in exercise, kinesiology, and rehabilitation facilities, typically without physician supervision, to assess fitness level and/or physiologic response to exercise and pose minimal risk. The study will take place in an exercise kinesiology and rehabilitation laboratory facility setting.

The study is a repeated measures model that will collect data on the participants with the designated HVT at four specified settings (Flow/FiO₂) during the Wingate exercise test and during the recovery interval. The Wingate exercise test configuration, equipment and procedures will be repeated for each HVT setting for a matched dataset. Participants who fit criteria will be asked to consent to enroll in the study.

The study will include four study arms, corresponding to four therapy settings being tested: (1) FiO₂=100% with Flow=5LPM, (2) FiO₂=21% with Flow=25-30LPM, (3) FiO₂=100% with Flow=25-30LPM, (4) FiO₂=21% with Flow=5LPM. The participants will wear the appropriately sized nasal cannula interface during the exercise and recovery.

V. Participant Enrollment

Participants will be solicited by investigators and consented prior to participation. Once consented, participants will be scheduled for their testing session(s) per protocol procedures. If enrolled, participants will be randomized to the order of the different settings on the HVT 2.0 device in different test sessions. Each participant will present on 4 different days for testing. This is to avoid fatigue related changes in sequential tests. Additional testing sessions may be scheduled to complete data collection if needed.

Sample Size:

Because no data exist for variance around these parameters, we will plan to enroll 15 participants, each to perform 4 test sessions.

Data Safety Monitoring:

Given that this protocol is a conventional exercise test protocol and therefore very low risk and routinely performed without physician oversight, there is no plan for a Data Safety Monitoring Board. Any adverse events (AE) will be promptly reported to the IRB for consideration.

VI. Study Procedures

Screening, Enrollment, & Management

During screening, participants will be asked to participate in this study, and if so, they will provide informed consent prior to enrollment. Participants will be instructed that if at any time during the study that they wish to discontinue the study, they are free to stop the testing and discontinue study participation at any time. All study procedures will be explained to the participant prior to starting any procedures, and all participants will be given a copy of the informed consent form.

Participants will be scheduled for test sessions to complete the objectives of the study and instructed to wear exercise appropriate clothing. Participants will be informed that prior to each test session, they should abstain from caffeine or tobacco products for a minimum of 4-hours, and alcohol and strenuous exercise for 10-hours ¹⁰. Participants are instructed that if at any time during the study he/she feels faint, dizzy, short of breath, or for any reason, they should stop the test.

Data collection during enrollment will include participant demographics (e.g., age, sex, height, weight). At each session, participant vital signs, lactate levels, dyspnea scores, work performance indices, and perception scores will be collected. The study will include four sessions, corresponding to four therapy settings being tested: (1) FiO₂=100% with Flow=5LPM, (2) FiO₂=21% with Flow=25-30LPM, (3) FiO₂=100% with Flow=25-30LPM, (4) FiO₂=21% with Flow=5LPM.

For each **test session** of the four HVT Settings, the following procedures will be followed.

Pre-Test Preparations:

Prior to starting the test, the participant will perform 2-3 second warm up sprints to acclimate to the ergometer. The cycle ergometer seating settings will be maintained consistent across all four therapy settings. Participants will be instrumented appropriately and initial data (e.g., vital signs, lactate, dyspnea) will be collected for baseline.

Wingate-type Exercise Test Procedures:

The exercise test model is called the Wingate anaerobic test. In a pre-test, the participants will Wingate test consists of pedaling with maximal effort for a series of short 8-second intervals against different loads, separated by 5 min of rest. This pre-testing is done to determine the load required for maximal power output. For the actual Wingate-type test, the participant will pedal as rapidly as possible for 60 sec against the load determined for maximal power output. Three indices of performance will be computed during the test period – peak power output, mean power output over the 60 seconds, and decrease in power (fatigue index).

At end of exercise interval, participant will be asked their perception of their level of exertion.

Recovery Interval:

Recovery interval will take place after exercise period up to 1 hour, or until participant is fully recovered and lactate levels approach baseline. A minimum of 15 samples during the recovery interval will be performed to complete lactate recovery data evaluation.

At end of recovery interval, participant perception of (1) Relief of Exertion at Recovery End, and (2) Comfort/Tolerance of Therapy will be recorded.

Sessions will be repeated on separate days, scheduled at the convenience of participant and laboratory, until a participant has completed a session at each of the HVT setting levels.

VII. Data Collection

Table 1. Key study data and collection points for each Phase of the Study.

	Study Start	After Warm-Up	Exercise Period q60sec	Recovery Period q5min	Study End
Participant pertinent Medical History	X				
Participant Vitals * (HR, RR, SpO₂, BP)	X	X	X	X	
Lactate [La]	X	X	X	X	
Dyspnea (Borg scale)	X	X	X	X	
Perception Scores (1-10 scale)					X
Work Performance			X		

*Vitals only measured prior to start of exercise, after exercise period ends, and after recovery interval. If practical, may record real-time the HR, RR, and SpO₂ with digital sensors. This will be completed for each Therapy Settings designated in the Study Protocol.

Data collection during enrollment will include participant demographics (e.g., age, gender, height, weight). Each Therapy Settings will collect the relevant participant vitals, lactate levels, dyspnea scores, and perception scores.

Primary Endpoint

- Change in lactate over (1) the exercise test interval, and (2) the recovery interval

Secondary Endpoints

- Participant Vitals: HR, RR, SpO₂, BP
- Dyspnea Score: modified BORG score, 1-10 scale
- Exercise Test Work Performance: peak power output, mean power output over 60 seconds, and decrease in power (fatigue index)

Tertiary Endpoint

Participant Perception of Performance/Recovery [1-10 scale]

- Level of Exertion at Exercise End: "How tired do you feel?"
- Relief of Exertion at Recovery End: "How fast do you feel you recovered?"

- Comfort/Tolerance of Therapy at Therapy Segment End: "How comfortable was the therapy while you had it on during exercise? How comfortable was the therapy while you had it on during recovery?"

VIII. Statistical Analysis

Participant demographics and characteristics will be summarized, compared, and appropriate statistical testing will be performed for the continuous and categorical variables. Descriptive analyses of the primary endpoints, supporting data/variables, and secondary outcome data will be performed. Assuming a non-normal data distribution for this study, a non-parametric test (e.g., Wilcoxon Signed Rank Sum test) will be performed with significance interval of 0.05 on all applicable variables. If continuous variables present a normal distribution, between-trial comparisons will be performed using two-way (within-within; trial* post-exercise sampling times) repeated measures ANOVAs. Otherwise, for the categorical variables, the Fisher's Exact test will be performed. Further analyses may be performed on the collected data based on ongoing analyses at time of study completion to identify additional relevant results.

IX. Risks and Discomforts

There are minimal or no known risks to the Wingate Anaerobic Exercise Test.^{12,13} Use of the high flow nasal cannula therapy by healthy persons has no known risks and has been used in the clinical setting for approximately seventeen years without known reports of adverse events related to the administration of high nasal flows when used according to manufacturer's recommendations. Prior work indicates that approximately ≤ 4 cmH₂O of distending pressure may be generated in the upper airway^{14,15} which is well below any known threshold for injury. In addition, it has been demonstrated that delivery of high flows of conditioned gas from a nasal cannula has a positive effect on airway mucosal function^{16,17}. Blood lactate measurements will be made using 1-2cc of whole blood from finger sticks (similar to blood glucose measurements using a glucometer). Fingers will be wiped with alcohol pads prior to sticking and sterile capillary tubes will be used for each sample. Alternatively, blood samples will be collected from a venous catheter in a prominent arm vein for enzymatic and/or lactate meter measurement of blood lactate concentration.

For these reasons, we have determined that this study represents a minimal risk and discomfort to the participants. The is the expected discomfort related to standard exercise and performance testing in exercise physiology laboratories.

X. Potential Benefits

Participants will receive no direct health benefit from participation. The trial may result in knowledge that leads to improvements in the quality of care, participant experience and ultimately cost of care associated with the care for participant with respiratory disease or those needed physical rehabilitation. Participants may receive up to \$50 per hour for participation, paid at the end of their participation.

XI. Monitoring and Quality Assurance

The clinical trial site will be monitored in accordance with policies at Vapotherm and those federal regulations that pertain to clinical research, namely 21 CFR Parts 50, 54, 56 and 812 and others as applicable. Monitoring will occur at regular frequency by the PI or designee, such as to allow ongoing review of data collected, site qualifications and compliance with the protocol. All investigators and study staff will be appropriately trained to ensure compliance with the protocol.

XII. Protocol Deviations

Any deviations from the Data Collection plan identified during monitoring or through other means will be documented on appropriate case report forms. These deviations include, but are not limited to items such as the following:

- Deviation from procedural sequencing, per protocol
- Failure to complete initial participant data collection
- Failure to capture/record physiologic readings at required/prescribed intervals

If the study site demonstrates a pattern of consistent and frequent deviations, the Sponsor will undertake appropriate activities (e.g., re-training) to attempt to bring the site into compliance with the protocol. A pattern of repeated serious deviations from the protocol may result in site termination from the study.

XIII. Adverse Event Reporting

During the course of the participant's participation in the study, the investigator will determine whether any adverse events have occurred. For the purposes of this protocol, an adverse event is any undesirable clinical/medical occurrence in a participant that is or is not attributed to the device or procedure required by this protocol. If any adverse event occurs, either anticipated or unanticipated, the investigators will immediately contact the sponsor's representative (site monitor) indicated on page 1.

XIV. Confidentiality

Rigorous procedures will be followed to maintain confidentiality of participant identification and test-related information and to adhere to government regulations concerning privacy. The privacy rules and requirements according to governing regulations will be adhered to. Participants will be assigned a study ID number. Only the data collection form and medical history form will link the participant's name to their ID number. These forms, along with consent forms, will be locked in [name] office and will only be accessed by him or involved study personnel. Assigning participant ID numbers and aliases to participant names on data collection and medical history forms will be performed in order to facilitate testing procedures.

When data collection is complete, all linking information to participant identity will be destroyed.

All Vapotherm representatives involved in this study will only have access to the participants' unique identification number throughout the study.

Confidentiality will be protected and maintained to the extent allowed by law.

XV. References

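### The trial is declared unblinded although oxygen fraction could probably be masked from participants at equal flow; this leaves the two FiO₂ contrasts, and the check that the flow effect holds at both FiO₂ levels, open to expectation

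*Combined protocol and SAP*

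**What the plan says.** Section IV (Study Design) calls the study a "prospective, unblinded clinical trial of a Wingate-type Anaerobic exercise test". Neither that section nor any other says who would or would not know the setting in use, and none gives a reason for an open design.

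The settings are listed in Sections II, IV and VI: "1) FiO₂=100% with Flow=5LPM, (2) FiO₂=21% with Flow=25-30LPM" and "3) FiO₂=100% with Flow=25-30LPM, (4) FiO₂=21% with Flow=5LPM". Every participant receives all of them: "The study is a repeated measures model that will collect data on the participants with the designated HVT at four specified settings". Section V adds that "participants will be randomized to the order of the different settings on the HVT 2.0 device in different test sessions".

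The hypothesis in Section II is that HVT, "regardless of the oxygen concentration (i.e., FiO₂), will reduce the work of breathing and increase the lactate clearance rate".

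The outcomes are of three kinds:

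- **Effort-dependent (secondary).** In the test "the participant will pedal as rapidly as possible for 60 sec", and peak power, mean power and a fatigue index are computed from it.
- **Self-reported (secondary and tertiary).** These are the Borg score and the 1-10 perception items on tiredness, recovery and comfort, for example "How fast do you feel you recovered".
- **Assayed (primary).** This is the change in blood lactate.

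**The concern.** Flow is felt at the nose and cannot realistically be hidden. Oxygen fraction at the same flow is different: a participant may well be unable to tell the two gases apart unless told or shown.

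Each participant passes through all four settings and can compare sessions. If they know which session delivers 100% oxygen, they may pedal harder, or rate exertion, recovery and comfort differently, for reasons unrelated to the gas. Randomizing the order does not remove this, because the expectation attaches to the setting and not to its position in the sequence.

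Two results are at stake. One is the effect of FiO₂ at each flow. The other is the claim that HVT works irrespective of FiO₂, which depends on comparing the flow effect at the two oxygen levels. Section I says the pilot may supply foundational data for a larger study, so a distorted estimate could carry forward into that design.

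**Working it through.** The plan states no figure on this point, so there is none to reproduce. The sample of 15 in Section V comes with no effect size, SD or power.

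**Step 1: which contrasts could be masked.** From the settings list in Section IV:

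| Pair | FiO₂ (%) | Flow (LPM) | Differs in |
|---|---|---|---|
| 1 v 4 | 100 v 21 | 5 v 5 | FiO₂ only |
| 2 v 3 | 21 v 100 | 25-30 v 25-30 | FiO₂ only (nominally) |
| 1 v 3 | 100 v 100 | 5 v 25-30 | flow only |
| 2 v 4 | 21 v 21 | 25-30 v 5 | flow only |
| 1 v 2 | 100 v 21 | 5 v 25-30 | both |
| 3 v 4 | 100 v 21 | 25-30 v 5 | both |

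Hiding FiO₂ fully masks 2 of 6 pairs. The other 4 differ in flow and stay at least partly open. The match of 2 with 3 is only nominal because flow is a range, and no section fixes it within a participant.

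**Step 2: bearing on the hypothesis.** Write each setting's mean as its number. The flow effect is (3 − 1) at 100% oxygen and (2 − 4) at 21%. Whether it is the same at both levels is the interaction:

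(3 − 1) − (2 − 4) = 3 − 1 − 2 + 4 = (3 − 2) − (1 − 4)

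The right-hand side is the difference between the two maskable FiO₂ contrasts. An expectation effect of 100% oxygen that is equal at both flows cancels here; one that differs by flow does not. In the separate FiO₂ contrasts it does not cancel in either case.

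**Step 3: which outcomes are exposed.** Power is volitional, and the Borg and perception scores are self-reported, so both are directly exposed. Lactate is an objective assay; expectation can reach it only through the effort that produced it.

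**Step 4: illustration of scale (assumed bias, not evidence of bias).** Inputs: n = 15 (Section V); α = 0.05 (Section VIII), taken as two-sided because the plan does not say; a paired t-test as a simple stand-in for the planned tests; true effect zero; and an assumed expectation shift of d SDs of the paired difference. The rejection probability is P(|T| > t₀.₉₇₅,₁₄), where T is noncentral t with 14 df and noncentrality d√15.

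| d (assumed) | d√15 | P(p < 0.05) |
|---|---|---|
| 0 | 0 | 5% |
| 0.2 | 0.77 | 11% |
| 0.3 | 1.16 | 19% |
| 0.5 | 1.94 | 44% |

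The documents give no basis for choosing any of these values of d.

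**The case against.** The strongest reply is that masking FiO₂ protects the less important contrasts. The hypothesis is mainly about flow. The flow-only pairs are 1 v 3 and 2 v 4, and they stay open whatever is done about FiO₂. Section VIII names no FiO₂ contrast as a test of interest. This largely stands: a reader might infer that masking FiO₂ would secure the trial's main comparison, and it would not. It still helps with the FiO₂ contrasts, and with the interaction behind the claim that oxygen concentration does not matter.

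A reader might also infer that participants are told, or can see, that they are breathing 100% oxygen. The documents do not say so. They contain the single word unblinded and describe neither what participants are told nor where the display sits. For the same reason, the feasibility of masking is an inference. The note to Table 1 allows real-time SpO₂ recording, which could reveal the setting if the participant sees it, so hiding the device display alone would not be enough.

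Coding lactate samples has limited value. Section IX allows finger-stick and lactate-meter measurement, and Section VI lets recovery end as lactate nears baseline, so many values are likely to be read in the session by staff who know the setting. Codes help only for samples assayed afterwards.

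Finally, this is an openly declared pilot of 15 participants with an objective primary endpoint. That limits the severity. It does not explain why a cheap partial safeguard is left out.

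**Conclusion.** The point holds in a limited form, as a worthwhile improvement and not an error in the plan. The trial is unblinded, two pairs of settings nominally differ only in FiO₂, and several outcomes depend on effort or self-report. Expectation could therefore affect power, Borg and perception scores, and lactate indirectly, in contrasts 1 v 4 and 2 v 3 and in the comparison of the flow effect across FiO₂ levels.

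The size of any bias cannot be derived from the documents; the percentages in the illustration rest on assumed shifts. The conclusion assumes that participants could not otherwise tell the oxygen fraction at a fixed flow and that the display can be kept out of sight.

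A reader might infer that the primary endpoint is unreliable because the trial is open. The documents do not support that: lactate is assayed, and its exposure is only through effort.

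**What to change.** In Section IV, replace the description of the trial as unblinded with a statement that participants are masked to FiO₂ and that flow is open. Then add to Section VI:

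- participants are not told the FiO₂;
- the device display and any SpO₂ readout are kept out of the participant's view in all four sessions;
- a given participant receives the same flow in settings 2 and 3;
- lactate samples assayed after the session carry a session code and not the setting;
- the operator remains unmasked for safety.

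In Section VIII, state that masking is partial, that the flow contrasts (1 v 3, 2 v 4) remain open to expectation bias, and that effort and self-reported results will be interpreted with that in mind. If masking FiO₂ proves impractical, say why and label those results exploratory.

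The cost is a screen, coded labels and a few lines of text. Sample size, number of sessions and the four settings do not change. The remaining weakness is that an unmasked operator who also collects scores could still cue the participant.

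### Each setting is on during the all-out test as well as recovery, so a raw lactate change cannot separate clearance from production; a clearance measure should be prespecified

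*Combined protocol and SAP*

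**What the plan says.** - **Target.** Section II hypothesises that the therapy "will reduce the work of breathing and increase the lactate clearance rate during exercise and recovery intervals".
- **Timing of therapy.** Section IV collects data "at four specified settings (Flow/FiO₂) during the Wingate exercise test and during the recovery interval", and adds: "The participants will wear the appropriately sized nasal cannula interface during the exercise and recovery".
- **Exercise dose.** Section VI (Wingate-type Exercise Test Procedures): "the participant will pedal as rapidly as possible for 60 sec against the load determined for maximal power output". Load and duration are set; work is not. Peak power, mean power and the fatigue index are secondary endpoints in Sections II and VII.
- **Primary endpoint, Section II (Aim #1).** "The primary endpoint is change in blood lactate from before the exercise test to recovery over a period of 30-60 minutes post-exercise".
- **Primary endpoint, Section VII.** "Change in lactate over (1) the exercise test interval, and (2) the recovery interval".
- **Analysis, Section VIII.** A non-parametric test such as the Wilcoxon signed rank "will be performed with significance interval of 0.05 on all applicable variables", or a two-way repeated measures ANOVA (trial by post-exercise sampling time) if data are normal. Neither has a term for work or end-exercise lactate. No rate constant, half-time or fraction remaining is defined anywhere.

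**The concern.** Lactate in recovery depends on how much was produced and on how fast it is removed. Because the setting is active while lactate is being produced in a maximal effort, it may act on both. The plan itself lists power output as an outcome, so it allows that work may respond to the setting. The trial is also unblinded, so expectation alone could change effort.

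The safeguards in the plan do not remove this. Repeating the same configuration and procedures matches the load, not the work. Randomised order balances order effects, not an effect of the setting on work. Separate days deal with fatigue.

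What is at stake is the label put on the result. Section II says the endpoints will establish the effect on lactate clearance, and the introduction says the pilot may feed a larger study. A production difference read as a clearance difference, or a clearance gain hidden by extra production, would carry forward.

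**Working it through.** The plan gives no lactate level, half-time, variance or expected work difference, and Section V says that no variance data exist. There is therefore no figure of the plan's to reproduce, and every input below is an assumption.

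**Model.** Lactate above baseline at t minutes after exercise is E(t) = A × 0.5^(t/h), where A is the end-exercise rise (production) and h is the half-time (clearance). This assumes a steady proportional fall from the end-exercise sample.

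**Inputs.** Control: A = 10 mmol/L, h = 20 min. Helpful setting: h = 19 min, a rate 20/19 = 1.053 times that of control. Extra production: 5%, so A = 10.5.

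**Section II endpoint (change from before exercise, mmol/L):**

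| Case | 30 min | 60 min |
|---|---|---|
| Control (A = 10, h = 20) | 3.54 | 1.25 |
| More production only (A = 10.5, h = 20) | 3.71 | 1.31 |
| Helpful (A = 10, h = 19) | 3.35 | 1.12 |
| Helpful, more production (A = 10.5, h = 19) | 3.51 | 1.18 |

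At unchanged clearance, the setting with more production looks 5% worse at both times. For the helpful setting, the unrounded gain at 30 min shrinks from 0.188 to 0.021 (11% of it left). At 60 min it shrinks from 0.130 to 0.074 (57% left).

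**Break-even extra rise**, 0.5^(t/20) / 0.5^(t/19):
- 30 min: 0.3536 / 0.3347 = 1.056, so the sign reverses above about 5.6%.
- 60 min: 0.1250 / 0.1120 = 1.116, so the sign reverses above about 11.6%.

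For a 10% higher clearance rate the break-even is 2^(0.1t/h). With h = 20 it is 11% at 30 min and 23% at 60 min. Over h = 25 to 15 it runs from 9% to 15% at 30 min and from 18% to 32% at 60 min.

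**Section VII recovery interval (fall from end of exercise to 30 min, A − E(30)):**
- Control: 10 − 3.54 = 6.46.
- More production, clearance unchanged: 10.5 − 3.71 = 6.79.
- Helpful, production unchanged: 10 − 3.35 = 6.65.

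The fall scales with its starting value. Here 5% more production with no clearance benefit gives a larger fall than the real shortening of half-time does.

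**Trial-by-time ANOVA.** With h = 20 in both, curves starting at 10 and 10.5 differ by 0.50 at the start and by 0.50 × 0.3536 = 0.18 at 30 min. They are not parallel although clearance is identical, so an interaction on the raw scale does not isolate clearance.

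**Normalised measure.** The fraction of the end-exercise rise left at 30 min is E(30)/A: 0.354 for control and 0.335 for the helpful setting, whatever A is.

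**The case against.** Several points on the other side are fair.

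- **The combined effect is part of the question.** The hypothesis covers exercise and recovery, and work of breathing too. A reader might infer that applying therapy during exercise is a design error. The documents do not support that: the timing matches the stated aim. Only the label of clearance on a raw change is at issue.
- **Section VII separates the phases.** A reader might infer that the primary measure ignores end-exercise lactate throughout. That is true only of the Section II wording. In Section VII that value is the natural end of the exercise change and start of the recovery change, so a production difference would show. What remains there is narrower: the raw fall scales with its starting value.
- **The recovery course is sampled and work is reported.** At least 15 recovery samples, a trial-by-time analysis and the power indices are planned, so an imbalance would be visible. Seeing it does not correct the lactate contrast, and no rule says how it would bear on interpretation.
- **The size is unknown.** A reader might infer that a helpful setting will look worse. The 5% illustration shows masking, not reversal (3.51 against 3.54), and more than half the gain survives at 60 min. The documents give no basis for expecting any particular work difference.
- **This is a pilot.** That limits the consequences, but a pilot meant to identify suitable parameters is a good place to define the clearance measure.

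**Conclusion.** The point holds as one of measurement and interpretation. The plan states a hypothesis about clearance rate, applies the setting while lactate is produced in an effort of unfixed work, and tests a raw change that responds to both production and clearance. The direction of distortion depends on which of the two primary definitions is used: extra production looks worse under Section II and better under the Section VII recovery interval.

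The size cannot be taken from the documents. Under the assumed 10 mmol/L rise and 20-min against 19-min half-times, 5% extra production hides most of the benefit at 30 min and somewhat under half of it at 60 min. Reversal needs more than about 5.6% and 11.6% extra rise respectively. If production does not differ by setting, the bias is absent. The change is worth making because it is cheap, not because a distortion has been shown.

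**What to change.** Keep therapy in both intervals and keep the raw lactate contrasts. Then:

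1. Reconcile the primary endpoint in Section II with that in Section VII, and name which pre-exercise sample is the baseline (Table 1 has one at study start and one after warm-up).
2. In Sections VII and VIII, prespecify one within-session clearance measure from the recovery samples: either a fitted recovery rate constant, or the fraction of the end-exercise rise above baseline remaining at a fixed time such as 30 min. Compare it between settings with the same paired or repeated-measures methods.
3. Base any statement about lactate clearance on that measure. Describe the raw change as the combined effect on production and recovery.
4. Report total work (mean power × 60 s) and end-exercise lactate by setting beside it. A work-adjusted model may be shown as supportive, but not as a condition for claiming an effect: work is measured after therapy starts, and it would miss a change in lactate produced per unit of work.

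The cost is a few lines of text and one derived variable per session, from data already planned. The downside is some added measurement noise from the fit or ratio, which matters with 15 participants and is a reason to keep the raw contrasts alongside.
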